there are no computerized components of the model. In addition, the acquisition costs are affordable, with an initial investment of less than \$10,000 required to begin training.

Our preliminary data using the physical colonoscopy model and our SCOPE program have been encouraging. We have shown that SCOPE, based on the above four tasks, can be administered in less than 50 minutes per learner. We have identified the key metrics for incorporation into a scoring system and have accumulated validity evidence that the SCOPE scoring system objectively assesses the technical skills required to perform standard flexible endoscopy. For each of the four tasks, we have validity evidence that task scores reliably differentiate between novices, intermediates, and experts. Our data indicate that SCOPE is a reliable, simple program for simulating basic flexible endoscopy. SCOPE could be an ideal training platform to prepare for basic clinical endoscopy and FES testing.⁷⁻⁹

The goal of this proposal is to develop a proficiency based skills curriculum for FES using SCOPE. We will draw on the success of proficiency based training for FLS and apply the same methodologies to FES. A proficiency based skills curriculum for FES using SCOPE could help prepare learners for the FES examination and could foster the success of the entire FES program.

Hypothesis

Our hypothesis is that training to expert derived performance goals on a non-computer based flexible endoscopy simulator will allow a group of novice endoscopists to acquire a level of skill adequate to achieve a greater than 80% pass rate on the manual skills portion of the Fundamentals of Endoscopic Surgery (FES) assessment. After completing this proficiency based curriculum, these novice endoscopists will also demonstrate performance scores on the Global Assessment of Gastrointestinal Endoscopic Skills for Colonoscopy (GAGES- C) and Simulated Colonoscopy Objective Performance Evaluation (S.C.O.P.E.) assessments equivalent to intermediately experienced endoscopists (50 - 140 endoscopies). Finally, the group of novice endoscopists who complete this proficiency based curriculum will demonstrate significantly higher scores on FES, GAGES-C, and S.C.O.P.E when compared to a control group that simply undergoes repeat assessment without any formalized curriculum (to control for learning effect of repeated assessment).

Methods

Subjects: Two distinct categories of subjects will be needed:

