Data Analysis: For continuous variables, mean performance differences between pretest and posttest assessment within groups will be statistically assessed for significance using paired t-test. Mean performance differences between groups will be statistically assessed for significance with unpaired t-tests. Differences for multiple repeated measures during long term follow up will be assessed with repeated measure ANOVA. For proportions, rates of achieving a passing score on the FES assessment will be statistically assessed for significance using Fishers exact test or chi squared as appropriate.

Sample Size / Power Analysis

Samples size can be estimated using previous data for two of our primary endpoints stated in the hypothesis, GAGES-C and S.C.O.P.E. Previously published GAGES-C scores for novice and intermediate endoscopists⁶ showed a difference in means between the two groups of approximately 6, with a standard deviation in the novice group of 3.8 and intermediate group of 1.6. If we use a paired, two tailed t-test (since our subjects undergo a pre-test then a post-test) with alpha set at 0.05, estimated standard deviation of 5.5 and a power of 80%, then we need 9 subject to be able to reject the null hypothesis. Since the exact difference in performance improvement is unknown, Figure 1 shows sample size and power for a difference in means ranging from 3 to 6.

Similar calculations can be done using the S.C.O.P.E. score endpoint. Unpublished data currently undergoing peer review showed that for S.C.O.P.E score, novice and intermediate

endoscopists showed a difference in means between the two groups of approximately 115 with a standard deviation in the novice group of 94 and intermediate group of 62.⁹ If we apply the same paired, two tailed t-test with alpha set at 0.05, estimated standard deviation of 150 and a power of 80%, then we need 15 subject to be able to reject the null hypothesis. Since the exact difference in performance improvement is unknown, the graph below shows sample size and power for a difference in means ranging from 95 to 125.

[figure not shown]

Figure 2: Required sample size as a function of statistical power for differences in means between groups ranging from 95 - 125

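### The first-stated hypothesis, an FES pass rate above 80% in trained novices, has no matching test, confidence limit or power, so the claim has no error control

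*Protocol*

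**What the plan says.** The Hypothesis section makes three claims. The first is absolute and concerns one group: training should let novices "acquire a level of skill adequate to achieve a greater than 80% pass rate on the manual skills portion" of FES. The second is that GAGES-C and S.C.O.P.E. scores will match those of intermediate endoscopists. The third is that trained novices will outscore an untrained control group on all three assessments.

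For pass/fail results, the Data Analysis section has one sentence: "rates of achieving a passing score on the FES assessment will be statistically assessed for significance using Fishers exact test", or chi-squared where that is suitable. It names neither the groups nor the visits to be compared, and 80% does not appear in it. For continuous scores the same paragraph is more specific: paired t-tests within groups, unpaired t-tests between groups, and repeated measures ANOVA over follow-up.

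The Sample Size / Power Analysis section begins "Samples size can be estimated using previous data for two of our primary endpoints stated in the hypothesis, GAGES-C and S.C.O.P.E". The words about two of the primary endpoints imply that FES is a further one, but it gets no calculation. From the two t-test calculations the protocol arrives at 24 evaluable experimental subjects (30 recruited, 20% dropout) and describes this as well powered for differences in mean performance. The 12 evaluable controls (15 recruited) come from a similar analysis that is not shown. No FES pass rate is assumed anywhere.

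**The concern.** A claim that one group's pass rate exceeds a fixed 80% is a one-sample claim. Fisher's exact test, and chi-squared in its usual two-group form, ask whether two independent groups differ. A clear difference from controls is compatible with a trained pass rate well below 80%. A trained rate above 80% is also compatible with no significant difference, if controls do fairly well.

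The analysis named for FES pass rates therefore does not address the first-stated hypothesis. What remains is the observed proportion in about 24 people, with no rule for how far above 80% it must lie. At stake are the error rate of the benchmark claim and the reader's belief that the trial was sized to support it.

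**Working it through.** **Inputs from the protocol.** Benchmark 80% (Hypothesis). Evaluable subjects: 24 trained and 12 control; 30 and 15 recruited (Sample Size / Power Analysis). Two-sided alpha 0.05 is used for sizing. True FES pass rates are not given, so those below are assumptions shown as a range.

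**1. The protocol's own figures.** Paired t-test, noncentral t, two-sided 0.05:
- GAGES-C, difference 6, SD 5.5: the smallest n for 80% power is 9 (power 81.7%). This agrees with the protocol: "with alpha set at 0.05, estimated standard deviation of 5.5 and a power of 80%, then we need 9 subject".
- S.C.O.P.E., difference 115, SD 150: n = 15 gives 78.8% and n = 16 passes 80%. The stated 15 is close enough.
- Dropout: 24/0.8 = 30 and 12/0.8 = 15, both as stated.

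These figures are sound for what they cover. None of them concerns the FES pass rate.

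**2. If the claim rests on the observed rate.** Since 0.8 × 24 = 19.2, an observed rate above 80% means at least 20 of 24. With X ~ Binomial(24, p):

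| True pass rate p | P(X ≥ 20) |
|---|---|
| 80% | 0.460 |
| 75% | 0.247 |
| 70% | 0.111 |
| 60% | 0.013 |

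At 20/24 (83%), the exact 95% lower limit is 62.6%.

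**3. What the two-group test shows.** Suppose 14/24 trained and 1/12 control subjects pass. Fisher's p = 0.005, yet the exact 95% interval for 14/24 is 37% to 78%, wholly below 80%. With assumed true rates of 60% and 10%, Fisher's test at 24 versus 12 is significant in 85% of trials, although the benchmark is missed by 20 points. With true rates of 80% and 50%, it is significant in 34%.

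**4. A test that matches the hypothesis.** Exact binomial, H0: p ≤ 0.80, with 24 evaluable:
- P(X ≥ 22 | 0.80) = 0.115, which is too large. P(X ≥ 23 | 0.80) = 0.0283 + 0.0047 = 0.033. At one-sided 5% the cut-off is therefore 23/24, with size 3.3%.
- Power = p^24 + 24·p^23·(1 − p). At p = 0.90: 0.080 + 0.213 = 0.29. At 0.95: 0.292 + 0.369 = 0.66. At 0.966: 0.436 + 0.368 = 0.80.
- At one-sided 2.5%, which matches the two-tailed 0.05 used for sizing, the cut-off is 24/24 (0.80^24 = 0.005). Power at 0.95 is 0.95^24 = 0.29.

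**5. Dependence on the number evaluable.** At one-sided 5% and a true 95%, power is 66% at n = 24 and falls to 57% at n = 29, because the cut-off stays at n − 1. It jumps to 81% at n = 30, where 28/30 suffices (size 4.4%). The 81% is available only if nobody drops out, so the cut-off must be tied to the actual number evaluable.

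**6. Pairing.** FES is taken by the same people at pretest and posttest, and at 6 and 12 months by those who complete the curriculum. If passes rose from 12/24 to 18/24 with six gains and no losses, Fisher's test would give p = 0.135, treating the visits as independent groups. Exact McNemar gives 2 × 0.5^6 = 0.031.

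**The case against.** The strongest reply is that the pass/fail sentence is incomplete rather than wrong. Fisher's test suits the randomised comparison of training with control, which is a separate aim. The sentence names no groups, allows chi-squared as appropriate, and so does not exclude a one-sample chi-squared against 80%. A separate analysis plan might add an exact interval. Sizing on two endpoints with prior data also suggests that no FES figure was available. Finally, this is simulator-based educational research and the pass proportion is directly visible.

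Much of this stands. It does not remove the point: the protocol states the benchmark as a hypothesis, names the tests for FES pass rates without the benchmark value, and fixes the sample size on other endpoints.

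A reader might infer four stronger things that the document does not support:
- **That a false claim is likely.** No success rule is stated. Even the loosest one gives at most 46% over true rates up to 80%, falling to 11% at 70%. That is far above 5% but not more likely than not.
- **That the investigators would treat a significant Fisher result as proof of a rate above 80%.** Nothing says so, and a team that saw 58% would hardly claim it. The example in step 3 shows only that the two questions differ.
- **That Fisher's test is planned for pretest versus posttest pass/fail data.** This is not stated, and the paired t-tests show that the authors recognise pairing. The McNemar point is a clarification.
- **That the 80% aim is the lead endpoint.** It is listed first, but the primary endpoints are not ranked.

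**Conclusion.** The point holds in this form: the hypothesis of an FES pass rate above 80% has no matching analysis and no sample size, so any such claim would lack error control. An observed-rate rule would make the claim 46% of the time at a true 80% and 25% at a true 75%. Under a valid exact test at one-sided 5% with 24 evaluable, the main difficulty is low power: 29% at a true 90%, 66% at 95%, and 80% only near 96.6%. The more probable outcome of a proper test is therefore an inconclusive result. The description of the sample as well powered does not extend to this aim.

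The observed-rate rule and the true pass rates are assumptions, since the protocol gives neither. The absence of an 80% reference value, limit or rule, and the sizing on mean GAGES-C and S.C.O.P.E. differences alone, are read directly from the text.

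**What to change.** Before outcomes are seen, add to Data Analysis one of the following for the training group at posttest:

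1. An exact one-sample binomial test of H0: p ≤ 0.80, or the equivalent exact lower confidence limit, with alpha stated and the cut-off set by the number actually evaluable. At 24 this is 23/24 at one-sided 5%, or 24/24 at one-sided 2.5%. Give the power at assumed true rates of 90% and 95%.
2. A statement that 80% is a descriptive benchmark, reported as the observed rate with an exact 95% confidence interval and no claim of significance.

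In Sample Size / Power Analysis, say that the power statement covers mean GAGES-C and S.C.O.P.E. differences and not the 80% aim. Keep Fisher's exact test and name its comparison as training versus control at posttest. Specify exact McNemar for any within-subject pass/fail comparison between visits, in line with the paired t-tests for scores.

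The cost is protocol wording only, with no extra subjects. The downside is having to disclose that power for the benchmark claim is low unless the true pass rate is about 97%.

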Based on these evidence based estimates, a sample size of 24 experimental subjects would allow us to be well powered across a broad range of differences in mean performance. If we allow for a 20% drop out rate, since participation is completely voluntary, that would result in recruiting 30 novice experimental subjects. or 10 subjects / site. In a separate analysis conducted similar to the ones above (not shown), approximately 12 control subjects would be required to reject the null hypothesis between the experimental and control groups with an 80% power. Applying the 20% drop out rate to the control group brings the target subject recruitment to 15, or 5 / site.

Comparison of the ES group with other groups is not part of our hypothesis testing, as this group serves to establish the reference criteria for the GAGES assessment and the proficiency scores for S.C.O.P.E. An estimated recruitment of up to 10 subjects per site should be more than adequate to ensure a broad representation of the desired skill set.

SAGES RESEARCH GRANT APPLICATION BUDGET SHEET

09BudgetSheet

Detailed budget for 12 month period from __ Jul. 1, 2013 through Jun. 30, 2014.

Dollar amount requested (Omit cents) _____ 30,000

Total for the grant request may not exceed \$30,000.

* Salary funds should be used for staff required to execute the study, but should not be used for salary support for the primary investigator. If salary support exceeds 50% of the project budget, then specific justification is required.

**Funds requests for travel for the presentation of a SAGES funded study should be limited to \$1,000.

NAME	POSITION TITLE	TIME/EFFORT		SALARY	FRINGE BENEFITS	SUB-TOTALS
		%	Hrs/ Week			
1. [name]	Principal Investigator*	5	2			
2. [name]	Assoc. Investigator	4	1.5			0
3. [name]	Assoc. Investigator	4	1.5			0
CONSULTANT COSTS						
EQUIPMENT						
(List all Items&Total Equipment Cost)		Items				Subtotal
SUPPLIES						
(List all Items&Total Supplies Cost)		Items Kyoto Colonoscopy SCOPE Models (6 at \$2,500 each, total \$15,000), Colon Inserts (6 at \$1,000 each, total \$6,000), MacBook pro computer 13 inch (3 at \$1,300 each, total \$3,900), Mac Software \$660, Misc recording / simulator maintenance supplies \$190				25,750
TRAVEL**						
(List all Items & Total Cost)		PI site visit travel to Tulane and UMD two visits each \$3,250, SAGES meeting travel for presentation - \$1000				4,250
PATIENT CARE COSTS						
CONSORTIUM/CONTRACTUAL COSTS						

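### FES pass rates: at the planned 24 v 12 completers, one pre-named unconditional exact test (Boschloo's) would hold the 5% level and gain about 0 to 10 points of power over Fisher's test

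*Protocol*

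**What the plan says.** Under Data Analysis, the protocol states for proportions that "rates of achieving a passing score on the FES assessment will be statistically assessed for significance using Fishers exact test or chi squared as appropriate". It gives no rule for choosing and does not name the comparison. Both tests are for independent groups, and Phase II randomises novices 2:1 to training (NST) or control (NSC) with FES at posttest. NST v NSC is therefore the natural reading, though an inferred one.

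The Hypothesis section expects trained novices to "achieve a greater than 80% pass rate on the manual skills portion" of FES. That is a goal for the trained group alone. The hypothesis against control is worded as higher scores on all three assessments, and mean differences between groups go to unpaired t-tests.

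The Sample Size section sizes the trial on GAGES-C and S.C.O.P.E. means only. It concludes that "a sample size of 24 experimental subjects would allow us to be well powered" and that "approximately 12 control subjects would be required to reject the null hypothesis between the experimental and control groups with an 80% power". A 20% dropout allowance raises recruitment to 30 and 15. No power is given for the FES pass rate.

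**The concern.** With 24 and 12 subjects, the choice between these tests can affect the result. Fisher's test conditions on the total number of passes, which leaves few attainable p-values in a small table, so its true error rate falls well below the nominal 5%. Uncorrected chi-squared has no such guarantee and can go above 5%. A rule that picks between them by expected counts inherits something of both.

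Two things are at stake: power given up without need on a comparison for which the protocol states no power, and a choice of test that could be made after the data are seen. The first depends on the control pass rate, which the protocol does not give.

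**Working it through.** **Inputs.** 24 trained and 12 control completers, 20% dropout, 30 and 15 recruited (Sample Size). Two-sided alpha of 0.05 is stated only for the t-test sizing ("If we use a paired, two tailed t-test", "with alpha set at 0.05, estimated standard deviation of 5.5 and a power of 80"%) and is assumed to apply to pass rates too. A trained pass rate of 80% is the floor of the Hypothesis goal. Control pass rates of 10% to 50% are assumptions.

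**The plan's own figures first.** Paired t-test power is taken from the noncentral t with noncentrality (difference/SD)·√n.
- GAGES-C: previous data "showed a difference in means between the two groups of approximately 6", and the SD is 5.5. n = 9 gives 81.7% and n = 8 gives 75.4%, so the stated 9 is reproduced.
- S.C.O.P.E.: difference 115, "estimated standard deviation of 150 and a power of 80%, then we need 15 subject". n = 15 gives 78.8% and n = 16 gives 81.7%, so the stated 15 is one short, which is immaterial here.
- Dropout: 24/0.8 = 30 and 12/0.8 = 15.

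None of these figures concerns the pass rate.

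**Method for pass rates.** All 25 × 13 = 325 possible tables (a of 24 trained passing, b of 12 controls passing) were enumerated. For each test:
- Size is the maximum over a common rate p of Σ Bin(a; 24, p)·Bin(b; 12, p) over the rejected tables.
- Power is the same sum with the two arms' own rates.
- Boschloo's test uses Fisher's two-sided p-value as its ordering statistic and maximises the tail probability over p.
- The expected-count rule uses Fisher if the smallest expected count is below 5, and otherwise uncorrected chi-squared.

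**One table in full, 20/24 v 6/12.**
- Smallest expected count: 10 × 12/36 = 3.33.
- Chi-squared: 36 × (20×6 − 4×6)²/(24×12×26×10) = 331,776/74,880 = 4.43, p = 0.035.
- Fisher: the observed table has probability C(24,20)·C(12,6)/C(36,26) = 0.0386. Adding all tables no more likely gives p = 0.053.
- Boschloo: p = 0.032 when ordered by Fisher's two-sided p-value, but 0.0475 under a different two-sided definition.

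For 19 to 21 passes of 24, Fisher and chi-squared fall on opposite sides of 0.05 at three tables only: 19/24 v 5/12 (0.058 v 0.024), 20/24 v 6/12 (0.053 v 0.035) and 21/24 v 7/12 (0.086 v 0.047).

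**Maximum true two-sided error rate.**

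| Completers | Fisher | Chi-squared | Expected-count rule | Boschloo |
|---|---|---|---|---|
| 24 v 12 | 2.95% | 5.5% | 4.3% | 4.5% |
| 25 v 12 | 3.4% | 6.1% | 5.2% | 4.8% |
| 26 v 13 | 3.4% | 5.4% | 5.3% | 4.7% |
| 28 v 14 | 3.9% | 6.3% | 6.3% | just under 5.0% |
| 30 v 15 | 3.3% | 5.5% | 4.7% | 4.9% |

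**Power with 80% trained.**

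| Control rate (assumed) | 24 v 12: Fisher | Rule | Boschloo | 30 v 15: Fisher | Rule | Boschloo |
|---|---|---|---|---|---|---|
| 10% | 99.0 | 99.4 | 99.3 | 99.8 | 99.9 | 99.9 |
| 20% | 92.2 | 94.1 | 94.9 | 97.7 | 98.5 | 98.3 |
| 30% | 76.9 | 79.7 | 83.8 | 89.5 | 91.6 | 90.5 |
| 40% | 55.7 | 58.1 | 65.7 | 71.7 | 75.2 | 73.2 |
| 50% | 34.4 | 35.7 | 43.8 | 47.1 | 50.4 | 49.4 |

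At 24 v 12 Boschloo gains 0.3 to 10 points over Fisher and about 0 to 8 over the rule. With 80% trained, the rule sends the table to Fisher in 32% of trials at 10% control, 52% at 20%, 70% at 30%, 83% at 40% and 92% at 50%.

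**The case against.** The strongest reply is that nothing here is wrong. Fisher's test is valid, its conservatism is not a misstatement, and naming Fisher or chi-squared is ordinary practice that a SAP, not at hand, may refine. That stands: this is a choice between defensible methods.

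A reader might go further and infer that the two tests disagree at the plan's own target, so that a real effect would be missed. The documents do not support this. The target of more than 80% concerns the trained group alone. Disagreement also needs controls at 5 to 7 of 12 (about 42% to 58%), and no control rate is given. All three discordant tables have a smallest expected count of 2.7 to 4.0, so the usual convention would send each to Fisher and no conflict would arise. Nor does Boschloo rescue all three: 21/24 v 7/12 stays non-significant at about 0.08. The between-arm hypothesis is worded as scores, so calling the pass-rate contrast the trial's lead test is also inference.

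The size of the gain is fairly challenged too. If untrained novices pass at 20% or less, it is 0 to 3 points. It also depends on exact completer counts: at 80% v 40% it is 10 points at 24 v 12, but about 4 at 25 v 12, 2 at 27 v 13 and under 2 at 30 v 15. At 30 v 15 the expected-count rule keeps within 5% and is level with Boschloo or up to 2 points ahead.

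What this does not remove is that the same rule exceeds 5% at other completer counts the trial could reach, whereas Boschloo's test does not.

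**Conclusion.** The point holds as a modest improvement in efficiency and pre-specification. It is not an error in the plan, and the protocol's wording does not make the analysis invalid. At the protocol's own completer counts, Fisher leaves at least 5 − 2.95 = 2.05 percentage points of the 5% unused. Boschloo's test recovers about 7 to 10 points of power if controls pass at 30% to 50%, and 3 or fewer at 20% or below. Even then power at 40% to 50% control is only 44% to 66%, so the change does not make the comparison well powered.

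The conclusion rests on four assumptions: that the sentence covers NST v NSC at posttest, that two-sided 0.05 applies, that the trained rate is about 80%, and that completers are near 24 and 12.

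**What to change.** For this comparison, replace the Fisher-or-chi-squared sentence with: *Posttest FES pass rates in NST and NSC will be compared with Boschloo's unconditional exact test at two-sided 0.05, ordering tables by Fisher's two-sided p-value; the difference in pass rates will be reported with an exact unconditional 95% confidence interval.*

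The two-sided definition must be fixed in advance. As the worked table shows, it moves the p-value, and the guarantee of never doing worse than two-sided Fisher belongs to the ordering named here.

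The cost is one sentence, with no extra subjects or data. The test is in standard software. The downside is that it is less familiar to readers than Fisher's.

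### The only power calculation shown for GAGES-C and S.C.O.P.E. is for a within-arm pre-post test that matches no stated hypothesis and that retest learning alone can make significant

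*Protocol*

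**What the plan says.** The Hypothesis section makes three claims about novices who complete the curriculum:

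1. an FES pass rate above 80%;
2. GAGES-C and S.C.O.P.E. scores equivalent to those of intermediate endoscopists;
3. significantly higher FES, GAGES-C and S.C.O.P.E. scores than "a control group that simply undergoes repeat assessment without any formalized curriculum (to control for learning effect of repeated assessment").

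Phase II randomises novices 2:1 to training (NST) or control (NSC), and both groups take a pretest and a posttest.

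Data Analysis says that "mean performance differences between pretest and posttest assessment within groups will be statistically assessed for significance using paired t-test". It then gives unpaired t-tests for differences between groups and does not rank the two.

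Sample Size / Power Analysis calls GAGES-C and S.C.O.P.E. two of the primary endpoints and applies a paired test to each, introduced with the words "If we use a paired, two tailed t-test (since our subjects undergo a pre-test then a post-test) with alpha set at 0.05":

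- GAGES-C: earlier data "showed a difference in means between the two groups of approximately 6, with a standard deviation in the novice group of 3.8", and with "estimated standard deviation of 5.5 and a power of 80%, then we need 9 subject to be able to reject the null hypothesis".
- S.C.O.P.E.: "endoscopists showed a difference in means between the two groups of approximately 115 with a standard deviation in the novice group of 94", and with "estimated standard deviation of 150 and a power of 80%, then we need 15 subject to be able to reject the null hypothesis".

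From these it takes 24 trained subjects (30 recruited). It adds that a separate calculation, which it does not print, needs about 12 controls (15 recruited) for 80% power between the groups.

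**The concern.** The null hypothesis of the paired test is no change from pretest in one arm. Rejecting it shows that trained novices scored higher the second time. It cannot show why, because familiarity with the test and the effect of training both go into the same difference. The protocol recognises this: it gives the learning effect of repeated assessment as its reason for having controls, and Phase I uses three S.C.O.P.E. trials to allow for a simulator learning curve.

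So the sizing on the page belongs to a test that addresses none of the three claims. The test that does address the third claim has no printed inputs. Both tests are to be assessed for significance. If the paired test in NST is significant and NST v NSC is not, a report could present the first as evidence for the curriculum and lose the protection of randomisation.

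**Working it through.** **1. The protocol's own figures.** Paired t-test, two-sided 0.05, noncentral t with n − 1 degrees of freedom and noncentrality (difference / SD) × √n.

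- GAGES-C, n = 9: (6 / 5.5) × √9 = 3.27, critical t 2.306, power 81.7%. The stated 9 is reproduced.
- S.C.O.P.E., n = 15: (115 / 150) × √15 = 2.97, critical t 2.145, power 78.8%. Strictly 16 are needed, so the stated 15 is reproduced within one subject.
- Dropout: 24 / 0.8 = 30 and 12 / 0.8 = 15. Both match.

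**2. The paired test when only retesting raises scores.** The protocol gives no retest gain, so g, in SDs of the change score, is an assumed range. With n = 24 and no curriculum effect, noncentrality is g × √24 and critical t is 2.069. The table gives the chance of a significant result in favour of training.

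| Assumed retest gain | Noncentrality | Paired test significant |
|---|---|---|
| 0.2 SD | 0.98 | 15% |
| 0.3 SD | 1.47 | 29% |
| 0.5 SD | 2.45 | 65% |
| 0.8 SD | 3.92 | 96% |
| 2 GAGES-C points, SD 5.5 (0.364 SD) | 1.78 | 40% |
| 57.5 S.C.O.P.E. points (half of 115), SD 150 (0.383 SD) | 1.88 | 44% |

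An equal retest gain in both arms cancels in NST v NSC, so the unpaired test stays at 5%.

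**3. The randomised comparison at 24 v 12.** Unpaired t-test, 34 degrees of freedom, critical t 2.032. Noncentrality is (difference / SD) / √(1/24 + 1/12) = (difference / SD) / 0.3536.

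| Endpoint, difference, SD | Noncentrality | Power at 24 v 12 | Controls for 80% at 2:1 |
|---|---|---|---|
| GAGES-C, 6, 5.5 | 3.09 | 85% | 11 |
| S.C.O.P.E., 115, 150 | 2.17 | 56% | 21 (42 trained) |
| S.C.O.P.E., 115, 94 | 3.46 | 92% | 9 |

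The SDs of 5.5 and 150 enter the protocol's paired calculation, so they stand for SDs of change. Using them here corresponds to comparing change scores between arms. The 94 is the novice SD quoted for S.C.O.P.E. and stands for a comparison of posttest scores. The protocol does not say which comparison the 12 controls refer to. With 24 trained, 12 controls give at least 80% power for S.C.O.P.E. at 115 only if the SD is about 110 or less.

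**4. The two tests side by side.** On the printed S.C.O.P.E. inputs, the paired test with 24 subjects has noncentrality (115 / 150) × √24 = 3.76 and power 95%. The randomised comparison has 56%. A significant paired test beside a non-significant comparison with controls is therefore a realistic outcome.

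**The case against.** The case against is substantial in four places.

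- **Power against controls is claimed.** A reader might infer that only the pre-post test is powered. The document does not support that: it states 80% power between the groups with about 12 controls, and on the printed GAGES-C inputs 12 is enough. What stands is that the endpoint, difference and SD behind the 12 are not given, and that it does not follow from the printed S.C.O.P.E. inputs.
- **No test is called primary.** A reader might infer that the paired test is meant to decide whether the curriculum works. The protocol does not say so, and being listed first is not a ranking. The third claim is worded against controls, and the unpaired test is its natural test. An order of analyses is often left to the SAP, which is not at hand. Even so, the protocol itself fixes a significance test on within-arm change and rests its printed sizing on it.
- **The hypothesis is wider than a comparison with controls.** The pass-rate and equivalence claims concern the trained group alone. The paired calculation borrows the novice-to-intermediate difference as its effect, which is an understandable way to size that group. A pre-post test still establishes neither claim.
- **The retest gain is assumed.** The control group is a precaution and implies no particular size of gain. The 15% to 96% is conditional, and it is not a forecast that the paired test will be positive.

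**Conclusion.** The point holds in this limited form. The only sizing shown for GAGES-C and S.C.O.P.E. is for a test that is not among the stated hypotheses and cannot separate training from retest learning, and Data Analysis does not say which of its two tests decides. How often the paired test would mislead depends on an unknown retest gain: 15% to 96% of trials over 0.2 to 0.8 SD with 24 trained subjects and no curriculum effect.

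The randomised comparison is adequately powered for GAGES-C at a difference of 6 and SD 5.5 (85%). For S.C.O.P.E. at 115 it ranges from about 56% to 92% according to whether the SD is 150 or 94, and the document does not settle which applies. The trial is soundly designed to answer the control question. The defect lies in which test is sized on the page and in the unranked analyses. It should be corrected, but it does not invalidate the design.

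**What to change.** In Data Analysis, state that the randomised NST v NSC comparison is the deciding test for superiority to control on FES, GAGES-C and S.C.O.P.E. Keep the 80% FES pass rate and equivalence to intermediates as separate claims, not replaced by that comparison. Report pre-post changes within each arm as supportive estimates with 95% confidence intervals. They should not be read as evidence of a curriculum effect, and the two arms' paired p-values should not be compared.

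In Sample Size / Power Analysis, label the 9 and 15 as sizes for detecting pre-post change in the trained arm. State the between-group power at 24 v 12 for each endpoint, with the difference, the SD, and whether change or posttest scores are compared.

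These are wording changes and one printed calculation, and they need no new data. The downside is that the stated power may look less favourable, notably for S.C.O.P.E. If the SD of 150 is the right one, the sponsor would have to accept about 56% for that endpoint or reconsider the numbers (21 controls and 42 trained for 80% at 2:1).
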